Rationale: Dislocation is the leading reason for early revision surgery. To address the problem of dislocation, the dual-mobility (DM) cup was developed in France in the 1970's. This cup should provide more stability and biomechanically reduce the risk of dislocation. In the Netherlands, most DM cups are placed in specific patients, e.g. with cognitive impairment and for revisions due to recurrent dislocations. Despite the increased and, in some countries, broad use of DM cups, high quality evidence of their (cost)effectiveness is lacking. This study aims to perform a trial to fill this gap in knowledge. Much of the information needed to judge the effectiveness of DM cups is already incorporated in the Dutch Arthroplasty Register (LROI). This register lends itself perfectly for a nested RCT towards this aim.

Objective: The primary objective is to investigate whether there is a difference in the number of hip dislocations following primary total hip arthroplasty (THA), using the posterolateral approach, with a DM cup compared to a unipolar cup in elderly patients 1 year after surgery. The secondary objectives are: to investigate whether there is a difference in the number of revisions; to investigate what the cost-effectiveness and cost-utility is of a DM cup compared to a unipolar cup at 1 year follow-up; to investigate whether there is a difference in the number of hip dislocations and revisions between a DM cup and a unipolar cup 2 years after surgery; to investigate whether there is a difference in patient reported outcomes between a DM cup compared to a unipolar cup 1 and 2 years after surgery; to compare the number of hip dislocations, revisions and PROM data between patients in the randomized DM group and patients in an observational cohort DM group. Finally, long-term survival of DM and unipolar cups will be evaluated based on revision and mortality data registered in the LROI.

Study design: Prospective multi-center international wide within the European Union (EU), single blinded RCT, nested in the national registry.

Study population: Patients ≥ 70 years old, undergoing an elective primary THA. **Intervention (if applicable)**: The intervention group receives a THA with a dual mobility cup, the control group receives a THA with a unipolar cup.

Main study parameters/endpoints: Primary: The number of dislocations. Secondary: costs, patient reported outcomes and implant survival.

Nature and extent of the burden and risks associated with participation, benefit and group relatedness: In addition to the benefits from regular care, the primary hip arthroplasty procedure, patients might benefit from randomization to receiving a DM cup. DM cups are designed to reduce the risk of hip dislocation, compared to a unipolar cup. Patients may undergo more thorough follow-up than non-study patients and may benefit from this increased surveillance compared with regular care. The only burden associated with study

participation is the time needed to complete the cost questionnaires (all other outcomes are part of standard care).

INTRODUCTION AND RATIONALE

Dislocation is the leading reason for early revision surgery. In the Netherlands, 34.5% of all revisions within the first year after surgery, performed between 2010 and 2015, were due to dislocation.¹

Most dislocations occur during the first year after surgery, of which approximately half within the first three months after operation.²⁻⁵ Hip dislocation is a major problem that results in reduced functioning and a deterioration in quality of life⁶, especially in patients with recurrent dislocation who often need revision surgery. In order to establish value based health care for patients with hip osteoarthritis, hospitals within the Santeon network asked patients which outcomes are of value to them. The patients indicated that they feared hip dislocation and that its prevention is paramount to them [personal communication]. In addition to the negative consequences of dislocation for the patients, dislocations also increase healthcare costs.^{7;8} A single dislocation was estimated to add 19% to the hospital costs of an uncomplicated THA, and a revision surgery up to 148%.8 With an average cost for a primary THA of about €10.000 in the Netherlands, this implies additional costs after dislocation that range from €1.900 to €15.000 per case. To address the problem of dislocation, the dualmobility (DM) cup was developed in France in the 1970's. 10 The DM cup consists of two articulations between three different components; a metallic acetabular shell, a mobile polyethylene liner and a femoral head. The mobile polyethylene liner articulates both with the acetabular shell and the femoral head. This should provide more stability and biomechanically reduce the risk of dislocation. 11-14 Dislocation rates reported for the DM-cup range from 0 to 4.6%12;14-18 which seems slightly lower than the 0.5 to 6% reported for unipolar cups. 19-24 Also, the use of DM cups for revision surgery in patients with recurrent dislocation has shown promising results.^{2;25;26} The Dutch national arthroplasty registry (LROI) shows that in 2015 3.9% of all cemented cups was a DM cup.²⁷ These DM cups are mainly used in patients with specific characteristics, such as cognitive impairment (not able to follow restrictions after surgery) or neuromuscular diseases (spasms) or as a standard procedure for revision surgeries due to recurrent dislocations. Internationally, DM cups are used more widespread. For instance, in France DM cups are used in an estimated 30% of all THAs.²⁸ Potential disadvantages of DM cups are loosening, intra prosthetic dislocation and psoas impingement.^{29;30} In the Netherlands, most DM cups are placed because of specific patient characteristics.³¹ These characteristics might negatively affect the risk for dislocation and revision surgery compared to the general THA population. Nevertheless, several studies reported similar failure rates between DM and unipolar cups. 12;14;17;32

Version number: 7.0.,14-11-2023

Beside the type of hip implant used, surgical approach is known to affect the outcome of THA, including dislocations. Different surgical approaches have been developed and each has (potential) advantages and disadvantages. Currently, the posterolateral approach is used in 60% of all THAs in the Netherlands.³³ Advantages of this approach are good exposure and the preservation of abductor muscles. A disadvantage is that this approach seems to be associated with relatively high dislocation rates compared to other surgical approaches.^{21;34-37} However, with a soft tissue repair this might be diminished.³⁸ Other often used approaches are the straight lateral and direct anterior approach. They have a slightly lower risk for dislocation, but have also some disadvantages. The straight lateral approach is associated with abductor insufficiency, resulting in limping.^{39;40} The direct anterior approach has a longer surgical learning curve and a higher risk of complications like nerve injury, periprosthetic fractures and malpositioning of the stem.⁴¹⁻⁴⁵ Considering the disadvantages of other approaches, the posterolateral approach is often preferred. Therefore, many patients could benefit from interventions aimed at reducing dislocation risk after THA using the posterolateral approach.

Despite the increased and, in some countries, broad use of DM cups, high quality evidence of their effectiveness is lacking. Recent reviews did not identify any randomized controlled trial (RCT) comparing DM cups with unipolar cups. The existing studies are of low methodological quality and most of these were performed in France. In France DM cups are used in a broad population. So far only one cost-effectiveness study has been performed, also in France, showing that the DM cup results in cost savings compared with a unipolar cup. The quality of this study is also limited, largely because it is based on the previous mentioned effectiveness studies of weak quality. Additionally, the results of this cost-effectiveness study are not transferrable outside France.

In conclusion, randomized controlled trials are needed to establish the effectiveness and cost-effectiveness of DM cups for primary THA. This study aims to perform such a trial. As much of the information needed to judge the effectiveness and cost-utility of DM cups is already incorporated in the LROI, this register lends itself perfectly for a nested RCT towards this aim.

The purpose of this study is to investigate whether there is a difference in the number of dislocations after THA, using the posterolateral approach, with a DM cup or a unipolar cup in elderly patients. Moreover, we will perform a cost effectiveness and cost-utility analysis from a health care and societal perspective. Finally, we will compare patient reported outcomes between both groups. As the posterolateral approach is most frequently used but also associated with a (relatively) high dislocation rate, this study will focus on patients who are treated using that surgical approach.

1. OBJECTIVES

Primary objective:

To investigate whether there is a difference in the number of hip dislocations following primary total hip arthroplasty (THA), using the posterolateral approach, with a dual-mobility (DM) cup compared to a unipolar cup in elderly patients 1 year after surgery.

Secondary:

- To investigate whether there is a difference in the number of revisions 1 year after surgery.
- To investigate what the cost-effectiveness and cost-utility of a DM cup is, compared to a unipolar cup after primary THA, from the health care and societal perspective at 1 year follow-up.
- To investigate whether there is a difference in the number of hip dislocations and revisions following primary THA with a DM cup compared to a unipolar cup 2 years after surgery.
- To investigate whether there is a difference in patient reported outcomes following primary THA with a DM cup compared to a unipolar cup 1 and 2 years after surgery.
- To compare long-term (5 and 10 year) implant survival based on revision and mortality data from national joint registries.
- To compare the number of hip dislocations, revisions and PROM data between patients in the randomized DM group and patients in an observational cohort DM group.

2. STUDY DESIGN

Design

A prospective multi centre single blinded randomised controlled trial, nested in the national

Version number: 7.0.,14-11-2023 9 of 26

registry of orthopaedic implants to compare the number of hip dislocations following primary total hip arthroplasty (THA), using the posterolateral approach, with a dual-mobility (DM) cup compared to a unipolar cup.

All patients will be followed-up until 2 years after surgery, and after final study follow up, participants remain traceable in the national joint registry for evaluation of long-term survival and mortality.

A third arm (non-randomised) consists of patients that are not eligible for a unipolar cup and therefore will receive a dual mobility cup. See figure 1 for an overview.

[figure not shown]

Figure 1. Flowchart with the 3 study groups.

3. STUDY POPULATION

3.1 Population (base)

All patients at the outpatient clinics of participating centers, that meet the criteria to undergo an elective primary THA will be screened for the in- and exclusion criteria.

3.2 Inclusion criteria

To increase the generalizability of the results, wide inclusion criteria are used. In order to be eligible to participate in this study, a subject must meet all of the following criteria:

Inclusion criteria:

- Patients who are eligible for elective primary THA with a cup, with a 32mm or 36mm liner, for any indication.
- THA using posterolateral surgical approach.
- Patients ≥70 years old

- Adequate comprehension of written and spoken Dutch, Spanish or Swedish

3.3 Exclusion criteria

A potential subject who meets any of the following criteria will be excluded from participation in this study:

Exclusion criteria:

- Patients unable to complete PROMs
- Patients with dementia, epilepsy*, spasticity*, mental retardation or alcoholism.
 - If dementia or mental retardation is not already mentioned in the medical chart, this can be determined by doctors opinion.
- Patients not eligible for either a unipolar or a DM cup

3.4 Sample size calculation

Exact dislocation rates in the Netherlands are unknown. Based on previous studies and reviews, we assume that current dislocation rate for unipolar cups is 4% whereas DM cups result in 1% dislocation. $^{10;12;14;15;17;18;46}$ Power analysis indicates that a total sample of 976 (488 in each group) is needed to detect a difference in dislocations between 4% in the unipolar cup group and 1% in the dual-mobility cup group, using the chi-square test with 80% power and α =0.05. To account for loss to follow-up, 550 patients will be included in each group.

4. TREATMENT OF SUBJECTS

Randomized trial:

- Treatment group A:
 - 550 patients will receive a THA with a dual mobility cup.
- Treatment group B:
 - 550 patients will receive a THA with a unipolar cup.

4.1 Investigational product/treatment

THA with a dual-mobility cup vs. THA with a unipolar cup.

Version number: 7.0.,14-11-2023 11 of 26

There are no restrictions to a specific brand of implant. Participating hospitals can use the implants of the industries they usually work with. This study does not investigate any specific product, but rather the concept of DM cups. Both DM and unipolar cups have >95% 5 year survival rates and are commonly used in standard orthopedic care.³⁰

5. METHODS

5.1 Study parameters/endpoints

5.1.1 Main study parameter/endpoint

The total number of dislocations, regardless of type of treatment (i.e. closed repositioning or revision).

5.1.2 Secondary study parameters/endpoints (if applicable)

- Revision surgery of any component for any reason
- Patient Reported Outcome Measures (PROMs)
 The following PROMs are already collected in the LROI according to follow-up of the Dutch orthopaedic association (NOV). This standard follow-up occurs pre- operative, 3 months and 1 year postoperative. For this study one extra measurement will be done at 2 years postoperative.
 - Physical functioning of the hip, measured by:
 - Hip disability and Osteoarthritis Outcome Score Physical Short form (HOOS-PS)⁴⁸
 - Quality of life, measured by:
 - EuroQol 5 Dimensions (EQ-5D)⁴⁹
 - o Pain, measured by:
 - Numeric Rating Scale (NRS) for pain in rest rest and during weight bearing
 - Change in functioning, measured by:
 - An anchor question about change in functioning.

Added as extra question to the standard PROMs:

- Fear of hip dislocation on a 5 point Likert scale
 - Added at all follow-up moments
- Healthcare and societal costs related to hip dislocation or surgery.
 - Added at 3 months and 1 year postoperative.
- Education level

 Added as extra question to the PROMs at baseline: "What is the highest education level you achieved?" Answer options according to CBS classification.

- Awareness of type of cup that was placed
 - Added as extra question to the PROMs at all follow-up moments: "Do you know what type of cup was placed?", "If yes, how did you get this information?"
- Long term (5and 10year) implant survival and mortality based on national registry data.

5.1.3 Other study parameters (if applicable)

Covariates are:

- Sex
- Age
- ASA score
- BMI
- Brand cup
- Type of stem
- Type of anesthesia (general or spinal)
- Education level
- Awareness of type of cup that was placed

5.2 Randomisation, blinding and treatment allocation

After signing informed consent, the patients will be randomized in one of the two study groups. A total of 1100 Patients will be randomized into 2 groups: dual-mobility cup versus unipolar cup. Each group consists of 550 patients. The investigator (or his designated representative) will perform the randomization using an online randomization program (CASTOR). Variable randomization blocks of 2, 4 and 6 patients will be used, and we will stratify for center.

Patients will be blinded for group allocation. The principal investigator and the participating surgeons may divert from the randomization scheme based on intra-operative findings. Any deviation from the assigned treatment group will be reported as a deviation from the protocol.

Patients in treatment group C will take part in the cohort study. These patients are not eligible for a unipolar cup and will receive a dual mobility cup.

5.3 Study procedures

During the pre-operative visit at the outpatient clinic, patients who are potential candidates for this study will be screened to determine if they meet the inclusion / exclusion criteria. If the patient is eligible, the investigator (or his designated representative) informs the patient about the study and proposes study participation, according to GCP guidelines. If desired, an additional telephone appointment can be arranged. Patients must sign an ethical committee (METC) approved study informed consent form (ICF) prior to participating in any study specific activities. The ICF can be signed face to face by the patient and investigator, or the patient can sign the ICF remotely and send it to the investigator by mail (due to COVID-19 restrictions). Subsequently, the investigator can sign the ICF and send one version to the patient. The ICF will be stored in a locked closet in the participating center. Pre-operative data will be collected including: demographics and medical history, NRS for pain in rest and during weight bearing, HOOS-PS and EQ-5D. The patients are also asked to fill out questionnaires. See table 1 for an overview of all measurements and follow-up moments.

Evaluation moment	Pre-operative	Intra-operative	3 months	1 year	2 years
Preoperative data (screening)	х				
Surgical Details		х			
PROMs	х		х	х	х
Serious Adverse Events	Anytime				

Table 1: Overview of follow-up moments.

5.4 Withdrawal of individual subjects

Subjects can leave the study at any time for any reason if they wish to do so, without any consequences. They will be asked for the reason for withdrawal, but do not have to answer if they do not want to. Furthermore, the investigator can decide to withdraw a subject from the study for urgent medical or other reasons.

When a patient withdraws from the study, all data collected prior to the moment of withdrawing will be used for study analysis, unless the patient also withdraws consent for use of this data.

5.4.1 Specific criteria for withdrawal (if applicable)

Not applicable

5.5 Replacement of individual subjects after withdrawal

Subjects who withdraw from the study will not be replaced, as long as a minimum of 488 patients per group remains. Otherwise, additional subjects will be recruited.

5.6 Follow-up of subjects withdrawn from treatment

The study data of withdrawn patients will be used until the moment of drop-out, unless a patient objects to this.

Patients will be treated according to the best medical judgment of the orthopaedic surgeon, regardless of the study protocol or withdrawal from the study.

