7.4 Interim analysis (if applicable)

Interim analyses for the primary study outcome will be performed when 200 patients have reached the 3 months postoperative PROM evaluation point. In the interim analyses the number of dislocations in each group will be compared. A chi-square test will be used and in case the assumptions of this test are not met, Fischer exact test will be applied. To guard against a type 1 error, we use the O'Brien-Fleming approach. As only one interim analysis will be performed, the alpha for this analysis is set at 0.005. Testing will be done two-sided. Furthermore, we will take the number of revisions and SAE's in each group in consideration, but will not formally test for differences in these. Results of the interim analysis will be discussed with the steering committee, Van Rens Foundation and the ethical committee. In case of a statically significant and relevant higher number of dislocations in the DM group, or more revisions or SAE's, appropriate actions will be taken (such as an early termination of the study).

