9.5 Temporary halt and (prematurely) end of study report

The investigator/sponsor will notify the accredited METC of the end of the study within a period of 8 weeks. The end of the study is defined as the last patient's last questionnaire. The data collection in the national joint registry will continue, even after a temporary halt or (prematurely) end of this study.

Version number: 7.0.,14-11-2023

The sponsor will notify the METC immediately of a temporary halt of the study, including the reason of such an action.

In case the study is ended prematurely, the sponsor will notify the accredited METC within 15 days, including the reasons for the premature termination.

Within one year after the end of the study, the investigator will submit a final study report with the results of the study, including any publications/abstracts of the study, to the accredited METC.

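### Data use ends at drop-out for every withdrawn patient, without separating leaving the study from refusing further use of outcome records

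*Protocol*

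**What the plan says.** Section 5.6 states the rule for withdrawn patients: "The study data of withdrawn patients will be used until the moment of drop-out, unless a patient objects to this". Section 5.4 agrees with it: what was collected before withdrawal is analysed, unless the patient also refuses use of that material. Section 5.4 also lets the investigator withdraw a patient, on urgent medical or other grounds, with no condition that the patient has refused anything.

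Section 5.5 rules out replacement while at least 488 patients per group remain. Only below that floor does it say "Otherwise, additional subjects will be recruited".

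On follow-up, section 2 says that all patients are followed for two years after surgery, and that after this "participants remain traceable in the national joint registry for evaluation of long-term survival and mortality". Section 9.5 adds: "The data collection in the national joint registry will continue", also after a halt or the end of the study. The registry outcomes named in section 1 are revision and mortality. The primary endpoint in section 5.1.1 is wider, because it also counts dislocations treated by closed repositioning.

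Section 7.1 says that the handling of missing values is still to be defined.

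**The concern.** The only refusal of data use that section 5.4 recognises concerns data already collected. It does not ask whether a patient who leaves, or whom the investigator takes out, would still allow later outcomes to be read from existing records. All are treated alike: nothing after drop-out is used. A patient who dislocates in month eight after leaving in month four does not count as a dislocation in the 1-year comparison.

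If leaving is related to how the hip is doing, and differs between arms, the comparison among those who stay is no longer the randomised one. A later analysis plan cannot repair this fully. A missing-data method can model outcomes that were not collected, but it cannot recover them. The choice is made in the protocol and the consent form.

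The stake is larger than usual because the primary outcome is rare, so that a handful of unseen events matters. The trial is nested in a registry, which makes continued ascertainment of at least some outcomes cheap.

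**Working it through.** **Inputs.** From section 3.4: "we assume that current dislocation rate for unipolar cups is 4% whereas DM cups result in 1% dislocation"; the sample size was obtained "using the chi-square test with 80% power and α =0.05"; 488 per group are needed and 550 per group are to be included. Sidedness is stated only for the interim analysis (section 7.4: "Testing will be done two-sided") and is assumed for the sample size. A threshold of 0.05 is used below, with no allowance for the interim look.

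**1. The plan's own figure.** Uncorrected, with mean rate 0.025:

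n = [1.960·√(2·0.025·0.975) + 0.8416·√(0.04·0.96 + 0.01·0.99)]² / 0.03² = (0.4327 + 0.1850)² / 0.0009 ≈ 424.

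With continuity correction: n = (424/4)·[1 + √(1 + 4/(424·0.03))]² ≈ 488.4, or 489 rounded up. The stated 488 is reproduced.

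**2. Expected events and allowance for loss.**
- At 488 per group: 488·0.04 = 19.5 and 488·0.01 = 4.9, together 24.4.
- At 550 per group: 22 and 5.5, together 27.5.
- Allowance: 550 − 488 = 62 per group, and 62/550 = 11.3%.

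**3. What the 62 would hide at the planned rates.** Unipolar 62·0.04 = 2.5; dual mobility 62·0.01 = 0.6. Adding these back gives about 22 versus 5.5 of 550. With 22 versus 6 the Pearson p is 0.002, so loss unrelated to outcome does no harm to the conclusion.

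**4. Assumed adverse case.** Unseen dislocations occur among the lost dual-mobility patients only, with none among the lost unipolar patients. For equal groups of size n with a and b events, the Pearson statistic is X² = (a − b)²·2n / [(a + b)(2n − a − b)].

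| Unipolar vs DM | Unseen DM events | X² | Pearson p | Fisher p |
|---|---|---|---|---|
| 20/488 vs 5/488 (as observed) | – | 225·976/(25·951) = 9.24 | 0.002 | 0.004 |
| 20/550 vs 8/550 | 3 (4.8% of 62) | 144·1100/(28·1072) = 5.28 | 0.022 | 0.033 |
| 20/550 vs 9/550 | 4 (6.5%) | 121·1100/(29·1071) = 4.29 | 0.038 | 0.058 |
| 20/550 vs 10/550 | 5 (8.1%) | 100·1100/(30·1070) = 3.43 | 0.064 | 0.094 |

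Four unseen events suffice under Fisher's test and five under the uncorrected Pearson test. With a continuity correction, which the sample size appears to use, 20 versus 9 gives p=0.060, so four suffice there too.

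**5. Variant with losses in both arms.** Two unseen unipolar events (3.2% of 62) and six unseen dual-mobility events (9.7%) give 22/550 versus 11/550: Pearson 0.052, Fisher 0.076. With five dual-mobility events, 22 versus 10 gives 0.031 and 0.047, still significant.

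**6. Gain from full ascertainment.** Moving from 488 to 550 observed per group raises power from 85.2% to 89.1% (normal approximation without correction).

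**The case against.** **The adverse case is extreme.** It puts the dislocation rate among lost dual-mobility patients at 6.5% to 8.1%, against a planned 1%, with none among the lost unipolar patients. The documents give no drop-out rate by arm and no reason to expect that pattern. The 62 is a general allowance for loss to follow-up, not a forecast of withdrawals under section 5.6. The Introduction also puts about half of first-year dislocations in the first three months, so late leavers have already contributed much of their risk. All of this stands: the calculation shows sensitivity, not bias.

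**Missing data are deferred, and consent matters.** The method for missing values may sit in an analysis plan that is not shown, and its absence here is no fault. Where a patient refuses data use, stopping is right. Both stand, but neither covers patients who have refused nothing.

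**Stronger readings that the documents do not support.**
- A reader might infer that withdrawals are routinely made good with new patients. Section 5.5 says the opposite down to 488 per group. Below that it speaks of additional patients, and nothing says that those who left are removed from the analysis.
- A reader might infer that the registry already holds what is needed for the primary endpoint. It is named only for revision and mortality, and no section says that it records closed repositionings.
- A reader might infer that stopping questionnaires alone counts as withdrawal. Section 5.4 speaks of leaving the study and does not settle this.
- A reader might infer that unseen events would reverse the result. Even at 22 versus 11 the dual-mobility arm has half the dislocations. Significance is narrowly lost and the direction is unchanged.

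**Conclusion.** The point holds as a weakness in the withdrawal rule. Sections 5.4 and 5.6 stop data use at drop-out for every withdrawn patient, including those the investigator withdraws, and so must be reconciled with the two-year follow-up of all patients in section 2. The floor of 488 per group keeps the sample size up but leaves the outcomes of those who left unknown.

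Attrition bias may remain; the documents do not show that it will. About 24 expected events stand against up to 62 unobserved patients per arm. Four or five unseen dislocations concentrated in one arm would remove significance, whereas about 0.6 and 2.5 at the planned rates would not. This rests on the section 3.4 rates, on the full allowance of 62 being used, and on events confined to the lost dual-mobility patients. The change is worth making because it is cheap, and outcomes not collected cannot be recovered later.

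**What to change.** In sections 5.4 and 5.6 and in the consent form, define two levels of withdrawal: (a) from study participation or questionnaires, and (b) from use of registry or hospital records. State that withdrawal by the investigator is level (a) only.

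Unless the patient refuses (b), continue to ascertain to 1 and 2 years:
- revision and death from the registry;
- dislocation, including closed repositioning, from hospital records. The sponsor should first confirm that these are available at the participating centres, as the documents do not show it.

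Analyse all randomised patients in their allocated arm. In section 5.5, say that any extra recruits are added to those already randomised and never substituted for them. Align section 2 with the revised wording.

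Cost: amended protocol and consent text, and a small record check for withdrawn patients who allow it.
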